10.1.7 Data quality assurance

- All participant data relating to the study will be recorded on printed or electronic CRF (e-CRF) unless transmitted to the Sponsor or designee electronically (eg, laboratory data). The Investigator is responsible for verifying that data entries are accurate and correct by physically or electronically signing the case report form (CRF).
- Guidance on completion of CRFs will be provided in the relevant sponsor data management study document.
- The Investigator must permit study-related monitoring, audits, IRB/IEC review, and regulatory agency inspections and provide direct access to source data documents.
- Monitoring details describing strategy (eg, risk-based initiatives in operations and quality such as Risk Management and Mitigation Strategies and Analytical Risk-Based Monitoring), methods, responsibilities and requirements, including handling of noncompliance issues and monitoring techniques (central, remote, or on-site monitoring) are provided in separate study documents.
- The Sponsor or designee is responsible for the data management of this study including quality checking of the data.
- The Sponsor assumes accountability for actions delegated to other individuals (eg, Contract Research Organizations).
- Records and documents, including signed ICFs, pertaining to the conduct of this study must be retained by the Investigator for 25 years after the signature of the final study

report unless local regulations or institutional policies require a longer retention period. No records may be destroyed during the retention period without the written approval of the Sponsor. No records may be transferred to another location or party without written notification to the Sponsor.

10.1.8 Source documents

- Source documents provide evidence for the existence of the participant and substantiate the integrity of the data collected. Source documents are filed at the Investigator's site.
- Data reported on the CRF or entered in the e-CRF that are transcribed from source documents must be consistent with the source documents or the discrepancies must be explained. The Investigator may need to request previous medical records or transfer records, depending on the study. Also, current medical records must be available.
- The Investigator must maintain accurate documentation (source data) that supports the information entered in the CRF.
- Study monitors will perform ongoing source data verification to confirm that data entered into the CRF by authorized site personnel are accurate, complete, and verifiable from source documents; that the safety and rights of participants are being protected; and that the study is being conducted in accordance with the currently approved protocol and any other study agreements, ICH GCP, and all applicable regulatory requirements.

10.1.9 Study and site start and closure

The study start date is the date on which the clinical study will be open for recruitment of participants.

The first act of recruitment is the first site open and will be the study start date.

The Sponsor or designee reserves the right to close the study site or terminate the study or one or more cohorts at any time for any reason at the sole discretion of the Sponsor. Study sites will be closed upon study completion. A study site is considered closed when all required documents and study supplies have been collected and a study-site closure visit has been performed.

The Investigator may initiate study-site closure at any time, provided there is reasonable cause and sufficient notice is given in advance of the intended termination.

Reasons for study or cohort termination by the Sponsor, as well as reasons for the early closure of a study site by the Sponsor or Investigator may include but are not limited to:

- For study termination:
 - Information on the product leads to doubt as to the benefit/risk ratio
 - Discontinuation of further study intervention development
- For cohort termination
 - Early evidence of lack of benefit

- For site termination:
 - Failure of the Investigator to comply with the protocol, the requirements of the IRB/IEC or local health authorities, the Sponsor's procedures, or GCP guidelines
 - Inadequate or no recruitment (evaluated after a reasonable amount of time) of participants by the Investigator
 - Total number of participants included earlier than expected

If the study or cohort is prematurely terminated or suspended, the Sponsor shall promptly inform the Investigators, the IECs/IRBs, the regulatory authorities, and any contract research organization(s) used in the study of the reason for termination or suspension, as specified by the applicable regulatory requirements. The Investigator shall promptly inform the participant and should assure appropriate participant therapy and/or follow-up. He/she should also stop all screening activities pertaining to the study or the relevant cohort(s). Should the Sponsor decide to pause recruitment in a cohort to allow decision making, the Investigator should pause all screening activities until further notice.

If the study is early terminated the patients who are receiving and benefitting from study treatment as per Investigator judgment may continue study treatment provided by the Sponsor until protocol defined treatment discontinuation criteria are met. The patients who continue study treatment after early study termination should be followed for safety (ie, study treatment administrations, ongoing SAE/related AE, new related AE, AESI or SAE and their associated concomitant medications and lab if any) and end of treatment reason during this time period.

10.1.10 Publication policy

- The results of this study may be published or presented at scientific meetings. If this is foreseen, the Investigator agrees to submit all manuscripts or abstracts to the Sponsor before submission. This allows the Sponsor to protect proprietary information and to provide comments.
- The Sponsor will comply with the requirements for publication of study results. In accordance with standard editorial and ethical practice, the Sponsor will generally support publication of multicenter studies only in their entirety and not as individual site data. In this case, a coordinating Investigator will be designated by mutual agreement.
- Authorship will be determined by mutual agreement and in line with International Committee of Medical Journal Editors authorship requirements.

10.2 APPENDIX 2: CLINICAL LABORATORY TESTS

- The tests detailed in [Table 6](#) will be performed by the local laboratory.
- Protocol-specific requirements for inclusion or exclusion of participants are detailed in [Section 5](#).
- Additional tests may be performed at any time during the study as determined necessary by the Investigator or required by local regulations.

Table 6 - Protocol-required laboratory assessments

Laboratory tests	Parameters
Hematology ^a	Platelet count Hemoglobin Hematocrit White blood cell (WBC) count with differential: Neutrophils Lymphocytes Monocytes Eosinophils Basophils
Clinical chemistry ^a	Urea or blood urea nitrogen (BUN) Creatinine and eGFR (MDRD formula ^b) Glucose Potassium Sodium Corrected Calcium Phosphate Chloride Magnesium Bicarbonate ^c Aspartate aminotransferase (AST)/ Serum glutamic-oxaloacetic transaminase (SGOT) Alanine aminotransferase (ALT)/ Serum glutamic-pyruvic transaminase (SGPT) Alkaline phosphatase Total and direct bilirubin Total protein Lactate dehydrogenase (LDH) Albumin Amylase Lipase
Endocrine function tests ^d	Thyroid-stimulating hormone (TSH) Tri-iodothyronine (T3) Free thyroxine (FT4) Cortisol (preferably in the morning)
Coagulation	International normalized ratio (INR) or Prothrombin Time (PT) (or Activated Partial Thromboplastin Time [aPTT])
Routine urinalysis	
 Specific gravity, pH, glucose, protein, blood, ketones, and leukocytes by dipstick Microscopic examination (if blood or protein is abnormal)
Other screening tests	
 Follicle-stimulating hormone and estradiol may be used to confirm a postmenopausal state in women not using hormonal contraception or hormonal replacement therapy (HRT) Highly sensitive serum or urine human chorionic gonadotropin (hCG) pregnancy test (as needed for women of childbearing potential) ^e Serology (hepatitis B surface antigen [HBsAg], hepatitis C virus antibody), Hepatitis

B viral load, HCV RNA level, CD4 counts & HIV viral Load^f

- Troponin
- The results of each test must be entered into the e-CRF

NOTES:

- a Blood Chemistry/hematology should be done with an overnight fasting if possible (should not interfere with hydration requirements). It will be performed weekly on D1 pre-dose, D8 and D15 (D15 for participants who receive Q3W only) during Cycle 1, then on Day 1 of every cycle up to Cycle 12, then every other cycle during Treatment Phase. Visits and assessments on C1D2-D3 will be performed for participants in the safety run-in or participants who are hospitalized because of high tumor burden or at Investigator's discretion. During the Observation Period, it will be performed at Follow-Up Visit 1. It can also be performed as clinically indicated. In case of Grade ≥ 3 liver function abnormal tests, additional tests will be repeated every 2-3 days until recovery to baseline value.
- b Modification of Diet in Renal Disease (MDRD) equation: Glomerular filtration rate (mL/min/1.73 m²) = 175 × (Serum Creatinine)-1.154 × (Age)-0.203 × (0.742 if Female) × (1.212 if African American)
- c Bicarbonate or carbon dioxide (venous) (if bicarbonate or carbon dioxide are assessed only on arterial blood at site level, to be done only if clinically indicated)
- d Endocrine function tests will be performed every 2 cycles throughout the entire treatment period and at EOT. During the Observation Period, they will be performed at Follow-Up Visit 1. They can also be performed as clinically indicated.
- e Pregnancy Test: Women of childbearing potential must have a negative urine pregnancy test result within 72 hours prior to first IMP administration of each cycle, at EOT and every 30 (± 7) days until 120 days (or refer to the individual substudy protocol) after the last dose of study treatment. If urine pregnancy results cannot be confirmed as negative, a serum pregnancy test will be required. Pregnancy tests (serum and/or urine tests) should be repeated if required by local guidelines.
- f Participants with known HIV infection under antiretroviral treatment should have HIV viral load & CD4+ count done at screening to confirm controlled infection. Participants with known HBV hepatitis under treatment must have viral load determined at baseline to document controlled infection. Participants with positive serology against HCV must have determination of HCV RNA levels. The need for additional testing due to positive test results will be at the discretion of the Investigator. HIV serology at screening will be tested in any countries where mandatory as per local requirements (see [Section 10.7](#)).

Investigators must document their review of each laboratory safety report.

10.3 APPENDIX 3: AES AND SAES: DEFINITIONS AND PROCEDURES FOR RECORDING, EVALUATING, FOLLOW-UP, AND REPORTING

10.3.1 Definition of AE

AE definition

- An AE is any untoward medical occurrence in a patient or clinical study participant, temporally associated with the use of study intervention, whether or not considered related to the study intervention.
- NOTE: An AE can therefore be any unfavorable and unintended sign (including an abnormal laboratory finding), symptom, or disease (new or exacerbated) temporally associated with the use of study intervention.

Events meeting the AE definition

- Any abnormal laboratory test results (hematology, clinical chemistry, or urinalysis) or other safety assessments (eg, ECG, radiological scans, vital signs measurements), including those that worsen from baseline, considered clinically significant in the medical and scientific judgment of the Investigator (ie, not related to progression of underlying disease), eg:
 - Leading to IMP discontinuation or modification of dosing, and/or

- Fulfilling a seriousness criterion, and/or
- Defined as an AESI
- Exacerbation of a chronic or intermittent pre-existing condition including either an increase in frequency and/or intensity of the condition.
- New conditions detected or diagnosed after study intervention administration even though it may have been present before the start of the study.
- Signs, symptoms, or the clinical sequelae of a suspected drug-drug interaction.
- Signs, symptoms, or the clinical sequelae of a suspected overdose of either study intervention or a concomitant medication.
- "Lack of efficacy" or "failure of expected pharmacological action" per se will not be reported as an AE or SAE. Such instances will be captured in the efficacy assessments. However, the signs, symptoms, and/or clinical sequelae resulting from lack of efficacy will be reported as AE or SAE if they fulfill the definition of an AE or SAE.
- The signs, symptoms, and/or clinical sequelae resulting from lack of efficacy will be reported as AE or SAE if they fulfill the definition of an AE or SAE. Also, "lack of efficacy" or "failure of expected pharmacological action" also constitutes an AE or SAE.

Events NOT meeting the AE definition

- Any clinically significant abnormal laboratory findings or other abnormal safety assessments which are associated with the underlying disease, unless judged by the Investigator to be more severe than expected for the participant's condition.
- The disease/disorder being studied or expected progression, signs, or symptoms of the disease/disorder being studied, unless more severe than expected for the participant's condition.
- Medical or surgical procedure (eg, endoscopy, appendectomy): the condition that leads to the procedure is the AE.
- Situations in which an untoward medical occurrence did not occur (social and/or convenience admission to a hospital).
- Anticipated day-to-day fluctuations of pre-existing disease(s) or condition(s) present or detected at the start of the study that do not worsen.

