3 OBJECTIVES AND ENDPOINTS

Table 1 - Objectives and endpoints

Objectives	Endpoints
Primary	

 To determine the antitumor activity of SAR444245 with or without other anticancer therapies. 	
 Refer to individual substudy.
Secondary	

 To confirm the dose and to assess the safety profile of SAR444245 when combined with or without other anticancer therapies. To assess other indicators of antitumor activity. To assess the plasma concentrations of SAR444245 when given with or without other anticancer therapies. To assess the immunogenicity of SAR444245. 	
 Incidence of treatment emergent adverse events (TEAEs), dose-limiting toxicities (DLTs), serious adverse events (SAEs), laboratory abnormalities according to National Cancer Institute Common Terminology Criteria for Adverse Events (NCI CTCAE) V5.0 and American Society for Transplantation and Cellular Therapy (ASTCT) consensus gradings (1). Time to response (TTR) defined as the time from the first administration of investigational medicinal product (IMP) to the first documented evidence of PR or CR determined by Investigator per Lugano response criteria 2014 (2). Duration of response (DoR) defined as the time from first documented evidence of PR or CR until progressive disease (PD) determined by Investigator per Lugano response criteria 2014 (2), or death from any cause, whichever occurs first. Clinical benefit rate (CBR) including CR or PR at any time or stable disease (SD) of at least 6 months (determined by Investigator per Lugano response criteria 2014) (2). Progression free survival (PFS) defined as the time from the date of first IMP administration to the date of the first documented disease progression determined by Investigator per Lugano response criteria 2014 (2) or death due to any cause, whichever occurs first. Plasma concentrations of SAR444245. Incidence of anti-drug antibodies (ADAs) against SAR444245.
Exploratory	

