3.6.2 Adverse events

General common rules for adverse events

All AEs will be graded according to National cancer institute common terminology for adverse events (NCI-CTCAE version 5.0) and coded to a lower-level term (LLT), preferred term (PT), high-level term (HLT), high-level group term (HLGT), and associated primary system organ class (SOC) using the Medical Dictionary for Regulatory Activities (MedDRA) version currently in effect at Sanofi at the time of database lock. Cytokine Release Syndrome (CRS) and Immune effector cell associated neurotoxicity syndrome (ICANS) will be graded using ASTCT Consensus grading.

The AEs will be analyzed in the following 3 categories:

- Pre-treatment AEs: AEs occurring during the pre-treatment period.
- Treatment-emergent adverse events (TEAE)s: AEs that developed, worsened (according to the Investigator's opinion) or became serious during the treatment-emergent period
- Post-treatment AEs: AEs that are developed, worsened or became serious during the post-treatment period.

Similarly, the deaths will be analyzed in the pre-treatment, treatment-emergent and post-treatment periods.

The primary AE analyses will be on TEAEs. Pre-treatment and post-treatment AEs will be described separately.

An AE with incomplete or missing date/time of onset (occurrence, worsening, or becoming serious) will be classified as a TEAE unless there is definitive information to determine it is a pre-treatment or a post-treatment AE.

If the assessment of the relationship to IMP is missing for an AE, this AE will be assumed as related to IMP. Missing grade will be left as missing.

Multiple occurrences of the same event in the same participant will be counted only once in the tables within a treatment phase, using the maximum (worst) grade by treatment phase. Summaries will be provided for all grades combined and for grade ≥ 3 (including grade 5). Missing grades, if any, will be included in the "all grades" category.

The AE tables will be sorted as indicated in [Table 7](#).

Table 7 - Sorting of AE tables

AE presentation	Sorting rules
SOC, HLGT, HLT and PT	By the internationally agreed SOC order and by alphabetic order of HLGTs, HLTS and PTs.
SOC and PT	By the internationally agreed SOC order and decreasing frequency of PTs ^{a,b}
PT	By decreasing frequency of PTs ^a

a Sorting will be based on the AE incidence.

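### Master protocol 10.3.1 says in adjacent bullets that lack of efficacy is not an AE and that it is one, so TEAE incidence can depend on which bullet a site follows.

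*Protocol*

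**What the plan says.** Two consecutive bullets in master protocol 10.3.1, under the heading for events that meet the AE definition, deal with lack of efficacy or failure of expected pharmacological action.

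- First bullet: such an outcome "per se will not be reported as an AE or SAE", and "Such instances will be captured in the efficacy assessments".
- Second bullet: such an outcome "also constitutes an AE or SAE".

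Both bullets agree that signs, symptoms and sequelae "resulting from lack of efficacy will be reported as AE or SAE if they fulfill the definition of an AE or SAE".

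The list of events that do not meet the AE definition, in the same section, includes "The disease/disorder being studied or expected progression, signs, or symptoms of the disease/disorder being studied, unless more severe than expected". It does not mention lack of efficacy. Master protocol 8.3.7, on disease-related events that do not qualify as AEs, is marked not applicable. Section 10.3 of substudies 01 and 03 refers back to the master protocol, so Cohorts A and C1 inherit the same text.

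Incidence of TEAEs and SAEs is a secondary endpoint (master protocol section 3, SAP 1.2). SAP 3.6.2 defines TEAEs as "AEs that developed, worsened (according to the Investigator's opinion) or became serious during the treatment-emergent period" and has no rule for lack-of-efficacy terms.

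**The concern.** A site cannot follow both bullets for the same participant. One that follows the first records nothing on the AE page for lack of efficacy as such; one that follows the second records an AE. The SAP builds its tables from what was reported, so the difference passes into the TEAE summaries. If the outcome led to stopping treatment, it could also enter the table of TEAEs leading to discontinuation.

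Two things are at stake. The secondary safety endpoint could vary with site practice rather than with the drug. The same outcome could also be counted twice: once as efficacy failure in ORR, CRR and PFS, and once as an adverse event. The study is uncontrolled, so its safety profile is read from absolute incidences, and it matters that those have one meaning.

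**Working it through.** **1. Is there a rule of precedence?** The places that could settle the conflict, side by side:

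| Place | Bearing on lack of efficacy as such |
|---|---|
| Master protocol 10.3.1, first bullet | Not an AE or SAE; goes to efficacy data |
| Master protocol 10.3.1, second bullet | Is an AE or SAE |
| Master protocol 10.3.1, exclusion list | Excludes expected progression; silent on lack of efficacy |
| Master protocol 8.3.7 | Not applicable |
| Substudies 01 and 03, section 10.3 | Refer back to the master protocol |
| SAP 3.6.2 | Counts AEs as reported; no rule |

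None gives precedence. Neither bullet is limited to a product, cohort or setting. The text is in the current Appendix 3, not in an amendment log.

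**2. What differs between the bullets?** The rule on signs, symptoms and sequelae is in both. The second adds only the sentence that contradicts the first. The conflict is therefore confined to lack of efficacy itself.

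**3. The plan's own AE figure.** The only AE-incidence calculation in the design is the chance of seeing at least one case of a specific AE with N = 25, which is 1 − (1 − p)^25:

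- p = 1%: 22.2%
- p = 2%: 39.7%
- p = 5%: 72.3%

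These match section 9.2 of both substudies and SAP section 4. The point neither disputes them nor depends on them.

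**4. Can the effect be sized?** Not from the documents. It depends on the share L of participants for whom a site would enter lack of efficacy as an event, which is not given. For illustration only, assume such entries occur independently of other events. An AE category with incidence b then moves to b + (1 − b)L:

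| b | L = 1/25 | L = 5/25 | L = 10/25 |
|---|---|---|---|
| 5% | 8.8% | 24.0% | 43.0% |
| 20% | 23.2% | 36.0% | 52.0% |
| 50% | 52.0% | 60.0% | 70.0% |

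For example, 0.20 + 0.80 × 0.20 = 0.36. Both b and L are assumptions. The table shows that any L above 0 moves the rate unless b is already 100%, and that the shift shrinks as b rises.

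**The case against.** The case against does not deny the contradiction; it attacks the consequence, and much of it stands.

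- **Expected progression is excluded separately.** A reader might infer that under the second bullet every non-responder or progressor becomes an AE. Substudy 03's precision table runs from 1 to 9 responders of 25, which would give 25 − 9 = 16 to 25 − 1 = 24 participants (64% to 96%). The documents do not support that count. The exclusion of expected progression applies whichever bullet is followed. Non-responders include participants with stable disease, and stable disease of at least 6 months counts as clinical benefit (master protocol 9.4.3.3). The table illustrates interval width and does not forecast response. A similar count for Cohort A would borrow a response rate from anti-PD1 monotherapy, not from this combination.
- **SAEs need a seriousness criterion.** Master protocol 10.3.2 still applies, and non-response alone does not meet death, threat to life, hospitalization, disability or congenital anomaly. The SAE effect should be smaller than the TEAE effect. A surge of Grade 5 events is not a supported reading either: deaths are tabulated by reason, with progression separate from AE (master protocol 9.4.3.5).
- **Dose confirmation is largely protected.** DLTs come from a listed set and exclude events due to progression (master protocol 4.1). The DLT window is 21 days in Cohort A and 28 in Cohort C1. The first scheduled scan is at 63 ± 7 days, so no earlier than day 56. The later ad hoc DMC trigger requires treatment-related events of Grade 3 or higher.
- **Any-TEAE incidence may be near its ceiling.** The SAP counts participants with at least one event. In the first-in-human study, 7 of 11 participants (63.6%) on 24 µg/kg monotherapy had a Grade 4 lymphocyte decrease. Any shift would show more in narrower categories. Lack-of-efficacy entries would also be coded and visible by preferred term.
- **Missing causality adds little.** The SAP treats an AE with missing causality as related, but investigators must assess causality for every AE (master protocol 10.3.3).

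These points limit the effect. None says which bullet a site should follow.

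**Conclusion.** The plan is wrong as written. Master protocol 10.3.1 contains two incompatible reporting rules for lack of efficacy, both current, with no precedence stated anywhere and no SAP rule to harmonize the result. TEAE incidence, and less so SAE incidence, can depend on which bullet a site follows, and an efficacy outcome can be counted a second time as an adverse event.

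The conclusion that the rules conflict rests on the text alone and needs no assumption. The size does need one, and the documents do not supply it. The table under the working shows sensitivity, not an expected effect. The primary endpoints, the sample size and the stated precision and detection figures are unaffected.

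**What to change.** Delete the second bullet in master protocol 10.3.1. Nothing is lost, because the first already contains the rule on signs, symptoms and sequelae. The remaining rule is that lack of efficacy itself goes to the efficacy assessments, and its signs, symptoms or sequelae are reported when they meet the AE or SAE definition. Both substudies pick up the change through their existing cross-reference. Section 8.3.7 need not be rewritten.

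Notify sites of the single rule. The SAP gives 20-Dec-2021 as the date of first enrollment, so some records may already follow the deleted bullet. Identify any lack-of-efficacy terms in the database and show them separately in the AE tables. Do not remove or re-classify AEs or SAEs already reported.

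The cost is one deleted bullet, one site communication, one term search and a separate line in the AE tables.
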